17.3.2. Secondary Efficacy Analyses

The proportion of subjects achieving partial ($\geq 75\%$) clearance of AK lesions within their Treatment Field will be summarized by cohort and visit. The 95% confidence interval for the percentage will be calculated using the Clopper-Pearson method for binomial proportions.

The number of facial AK lesions in the Treatment Field, change from baseline values, and percent change from baseline values will be summarized by cohort and visit.

These analyses will be conducted on the modified Intent-to-Treat (mITT) population, mITT Face (mITT-Face) subpopulation, Per Protocol population (PP), and PP Face (PP-Face) subpopulation.

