6. STUDY OBJECTIVES

Primary Objective:

- To assess the percent of subjects with complete clearance of the actinic keratosis (AK) lesions in their Treatment Field at Week 16
- To assess the percent of subjects with facial Treatment Fields who achieved complete clearance of actinic keratosis (AK) lesions at Week 16
- To evaluate the systemic and local (skin) safety and tolerability of topical application of VDA-1102 ointment in adult subjects with AK for 12 weeks

Secondary Efficacy Objectives:

- To assess the percent of subjects with partial ($\geq 75\%$) clearance of the actinic keratosis (AK) lesions in their Treatment Field on Week 16
- To assess the percent of subjects with facial Treatment Fields who have partial ($\geq 75\%$) clearance of the actinic keratosis (AK) lesions on Week 16
- To assess the reduction in the number of the actinic keratosis (AK) lesions in the Treatment Field on Week 16
- To assess the reduction in the number of the actinic keratosis (AK) lesions on Week 16 of subjects with facial Treatment Fields Study Description

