8. STUDY ENDPOINTS

Primary Efficacy Endpoints:

- Percentage of subjects achieving complete clearance of AK lesions within their Treatment Field on Week 16
- Percentage of subjects with facial Treatment Fields achieving complete clearance of AK lesions on Week 16

Secondary Efficacy Endpoints:

- Percentage of subjects achieving partial ($\geq 75\%$) clearance of AK lesions within their Treatment Field on Week 16
- Percentage of subjects with facial Treatment Fields achieving partial ($\geq 75\%$) clearance of AK lesions on Week 16
- Change from baseline in the number of AK lesions in the Treatment Field of each subject by Weeks 16
- Change from baseline in the number of facial AK lesions in the Treatment Field of each subject by Weeks 16

Safety Endpoints:

- AEs, clinical laboratory parameters, vital signs, physical examinations, Local Skin Reaction (LSR) Scores, electrocardiograms, and drug exposure.

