17. STATISTICAL PLAN

17.1. Sample Size Rationale and Justification

The study is designed to evaluate the efficacy, safety, and tolerability of topical VDA-1102 ointment in subjects with actinic keratosis. Approximately 150 subjects will be enrolled in this 2-cohort clinical trial. In each cohort, approximately 75 subjects will be enrolled in order to complete each cohort with safety and efficacy data from at least 70 subjects who received study drug. Considering the results from a previous Phase 2 parallel, randomized, placebo-controlled study with a sample size of 29 to 32 subjects per treatment group, this sample size is considered adequate to evaluate the stated objectives. A formal sample size calculation was not performed.

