17.2. Statistical analysis

All measured variables and derived parameters will be listed individually and, if appropriate, tabulated by descriptive statistics. Data will be summarized by cohort and visit, if appropriate. Unless stated otherwise, the term “descriptive statistics” refers to number of subjects (n), mean, median, standard deviation (SD), minimum, and maximum for continuous data and frequencies and percentages for categorical data. The data will be analyzed using the SAS[®] version 9.4 or higher (SAS Institute, Cary North Carolina). Details of all statistical analyses to be performed will be included in the Statistical Analysis Plan (SAP).

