17.7.2. Modified ITT (mITT) Population

The modified Intent-to-Treat (mITT) population will be defined as all subjects who are enrolled into the study, received any study drug, and did not fail Exclusion Criterion #2. Subjects in this population will be analyzed according to the cohort to which they were allocated. All efficacy analyses will be performed on the mITT population.

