17.7.3. Per Protocol Population

Subjects without violations or major deviations will be included in the Per Protocol Population. All efficacy analyses will be repeated on this population.

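### Does the word 'facial' in the Section 17.3.2 lesion-count sentence leave the whole-field count endpoint without an analysis?

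*Combined protocol and SAP*

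**What the plan says.** Section 6 gives two secondary objectives on lesion counts. One concerns the whole field: "To assess the reduction in the number of the actinic keratosis (AK) lesions in the Treatment Field on Week 16". The other is the same quantity in subjects whose field is on the face. Section 8 and the synopsis carry the same pair as endpoints, the first being "Change from baseline in the number of AK lesions in the Treatment Field of each subject by Weeks 16" and the second its facial counterpart.

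Section 17.3.2 deals with counts in one sentence: "The number of facial AK lesions in the Treatment Field, change from baseline values, and percent change from baseline values will be summarized", for each cohort and visit. Its closing sentence runs the section's analyses on four populations: mITT, mITT-Face, PP and PP-Face.

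The population definitions do not restrict mITT or PP by field location. Of mITT, Section 17.7.2 says "All efficacy analyses will be performed on the mITT population"; of PP, Section 17.7.3 says "All efficacy analyses will be repeated on this population". Section 17.7.4 forms the Face populations from subjects whose field is on the cheeks or forehead. Inclusion criterion 3 in Section 9.1 allows fields on the balding scalp.

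Section 17.2 describes the statistics for a count ("number of subjects (n), mean, median, standard deviation (SD), minimum, and maximum for continuous data") and leaves further analysis detail to the SAP. The synopsis states that no formal efficacy testing is planned because there is no control arm.

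**The concern.** Two count endpoints are declared, but the section that specifies the analysis names only one of them, the facial one. It then applies that facial variable to two populations containing subjects who have no facial field. A programmer working from this sentence alone could restrict the mITT and PP count tables to facial lesions, and the whole-field endpoint would have no table under 17.3.2.

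The distinction is not idle in this programme. In the earlier Phase 2 study the whole-field reduction on 10% ointment was close to that on placebo, while the face-only subset looked better, and Section 5.6.4 says the present results will feed Phase 3 design and dose selection. A plan that reported only the facial count would leave out the less favourable of the two views.

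**Working it through.** The plan gives no figure to reproduce here, so the check is mainly a comparison of the text, with a small illustration of size.

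**1. How the other efficacy sentences are built**

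| Endpoint pair in Section 8 | Analysis sentence | Contains 'facial'? | Populations |
|---|---|---|---|
| Complete clearance, all and facial | 17.3.1 | No | mITT, mITT-Face, PP, PP-Face |
| Partial clearance, all and facial | 17.3.2, first paragraph | No | Same four |
| Change in count, all and facial | 17.3.2, second paragraph | Yes | Same four |

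In the first two rows one neutral sentence serves both endpoints: mITT and PP give the version for all subjects, and the Face subsets give the facial version. The third row has the same four populations and differs only by the adjective. If the variable were meant to be facial only, listing mITT and PP beside the Face subsets would serve no purpose.

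**2. Where the adjective can matter**

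A subject in mITT-Face or PP-Face has the whole field on the face, so the facial count equals the whole-field count. The two wordings therefore give identical Face tables. They can differ only in the mITT and PP tables, through scalp subjects.

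**3. Size under a literal reading**

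Inputs: 75 enrolled per cohort, with at least 70 providing data (Section 17.1). The facial share *s* in this trial is not stated. I assume 75%, the approximate share in the earlier Phase 2 study (Section 5.5.2), with 60% to 90% as an illustrative range that has no source in the documents.

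Scalp subjects per cohort = (1 − *s*) × *n*:

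- *n* = 75: 0.25 × 75 = 18.75, about 19; 0.40 × 75 = 30; 0.10 × 75 = 7.5, about 8.
- *n* = 70: 0.25 × 70 = 17.5, about 18; 0.40 × 70 = 28; 0.10 × 70 = 7.

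If scalp subjects were dropped, the mITT count table would hold about 75 − 19 = 56 per cohort (45 to 67), exactly the subjects of the mITT-Face table. Two tables with different population labels and the same contents would stand out at first review.

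One could also imagine scalp subjects kept and scored as having zero facial lesions. That needs a recoding rule the plan does not contain. Section 11.1.1 asks the investigator to count lesions within the Treatment Field, wherever it lies, and describes no separate facial count. A scalp subject's record holds that subject's actual count.

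**4. The intended table can be made**

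Because the whole-field count is collected at each efficacy visit, the mITT and PP tables need no data beyond those already planned. Percent change requires only a non-zero baseline, and inclusion criterion 3 calls for 4 to 8 lesions. A subject enrolled in breach of that criterion could stay in mITT, since Section 17.7.2 removes only undosed subjects and those failing Exclusion Criterion 2. Percent change would still be defined for that subject unless the baseline count were zero.

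**The case for a change.** The best argument for acting is that an analysis section should be right as written. The sentence repeats the wording of the facial endpoint in Section 8, so it can be read as naming that endpoint and forgetting the other. The earlier study shows that the two views can diverge: mean reductions were 32.1% against 27.8% on placebo overall, and 41.3% against 29.4% in the per-protocol face subset (Section 5.6.1). The correction would be one word. Nor can one confirm that the SAP settles the point, because no separate SAP text is in the file.

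What stands is that the adjective does not fit two of the four populations listed beside it. The rest does not carry. That 17.3.2 fails to name the whole-field count is not a defect in itself, because Section 17.3 does not name the facial clearance endpoints either and nobody would say they lack an analysis. The divergence in the earlier study is a reason to report both views, and the plan already provides for both: the synopsis puts the efficacy endpoints on mITT, PP and the face subgroups, and Sections 17.7.2 and 17.7.3 put all efficacy analyses on mITT and PP. Without SAP text one cannot say how the tables will be programmed, but that uncertainty gives no ground for predicting the wrong table when the rest of the protocol points to the right one.

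**Conclusion.** The concern is correct about the wording but calls for no change to the plan. It is a one-word clerical slip in the description of one secondary, descriptive summary. The endpoint list, the synopsis, the population definitions and the parallel clearance sentences all lead to the same reading: whole-field counts on mITT and PP, and the same counts in the Face subsets for the facial endpoint.

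No data are lost, no population or sample size is affected, and the primary and partial-clearance analyses are untouched. The figure of about 19 scalp subjects per 75 (8 to 30) shows how many would be missing from a literally programmed table. It rests on an assumed facial share carried over from a different trial, in which face meant simply not scalp, whereas here it means cheeks or forehead. It does not measure bias in any result, since such a table would visibly duplicate the Face table and the correct one could be run from the same dataset.

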17.4. Safety Assessments

The safety endpoint data will be summarized for the ITT population. AEs will be categorized by System Organ Class (SOC) and Preferred Terms (PT) using the Medical Dictionary for Regulatory Activities (MedDRA version 19.1 or higher). The incidence of AEs, as well as the intensity and relationship to study drug will be summarized by cohort. Safety will also be assessed by evaluating findings of physical examinations, vital signs, clinical laboratory test results, 12-lead ECG tracings, Local Skin Reaction Score, drug exposure, concomitant medications, Urine Pregnancy Test results, withdrawals/terminations, and dose adjustments. These findings will be summarized and compared to findings from baseline evaluations.

Local Skin Reaction (LSR) Scores will be summarized.

17.5. Pharmacokinetic Parameters

Not applicable.

17.6. Missing Data

Every effort will be made to obtain required data at each scheduled visit from all subjects who have been enrolled. Details regarding the handling of missing data will be presented in the SAP.

17.7. Data Sets

17.7.1. Safety Population

The Safety population will be defined as all subjects who are randomized and who receive study drug. Safety analyses will be performed on the Safety population.

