The safety endpoint data will be summarized for the Safety Population. AEs will be categorized by System Organ Class (SOC) and Preferred Terms (PT) using the Medical Dictionary for Regulatory Activities (MedDRA) version 19.1 or higher. The incidence of AEs, as well as the intensity and relationship to study drug, will be summarized by cohort. Safety will also be assessed by evaluating findings of vital signs, physical examinations, Local Skin Reaction Scores, clinical laboratory test results, 12-lead ECG tracings, drug exposure/compliance, concomitant medications, pregnancy testing, dose adjustments, and withdrawals / terminations. These findings will be summarized and compared to findings from Baseline (Day 1 Pre-Dose) evaluations.

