5.6.4. Study Design Rationale

The results from the Phase 2a (VDA-CP-03; Section 5.5.2) clinical trial support the safety and tolerability of 200 mg of 10% VDA-1102 ointment when applied once-daily for 4 weeks (28 days), but the efficacy was moderate. In the completed Cohort 1 of the ongoing Phase 1B trial (VDA-CP-04; Section 5.5.3) subjects treated with 10% VDA-1102 twice-daily for 8 weeks the efficacy was improved, while safety and tolerability were maintained. These studies suggest that higher study drug concentrations, more frequent dosing, and/or a longer treatment duration are likely to improve efficacy. The non-clinical and clinical data support the safety of this approach as well.

In Cohort 1 (**Part A**) of the current study 40 subjects will apply approximately 200 mg of 10% VDA-1102 twice-daily, the same dose applied in Cohort 1 of trial VDA-CP-04. However, subjects enrolled in the current study (VDA-CP-05) will apply the study drug to their Treatment Field for 12 weeks instead of 8 weeks.

Once approximately 40 subjects have been enrolled in Cohort 1 (Part A), this cohort will be closed to enrollment and Cohort 2 (Part B) will be opened for enrollment.

The reason for the initial split into Part A and Part B is due to the drug product manufacturer's schedule (i.e., drug supply).

In Cohort 2 (**Part B**) approximately 40 subjects will apply approximately 200 mg of 20% VDA-1102 once-daily to their Treatment Field for 12 weeks.

Following completion of enrollment of approximately 40 subjects into Cohort 2 (Part B), **Part C** will be opened to enrollment wherein 70 subjects will be randomized in a 1:1 ratio to either Cohort 1 or Cohort 2. Thus, the trial will close with a total of approximately 75 subjects in each cohort.

The goals and rationale of this open-label, dose-escalation trial are to assess the tolerance, safety, and efficacy of two different dosing strategies for VDA-1102 ointment. The results of this study will be applied to the study design and dose selection for the pivotal Phase 3 trials.

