12.1.2. Randomization

Subjects who pass screening and are eligible for enrollment will be consecutively enrolled into Part A (Cohort 1) and Part B (Cohort 2). There will be no need for randomization in Part A or Part B.

Subjects enrolled into Part C will be randomly assigned to Cohort 1 or to Cohort 2 at a ratio of 1:1 to allow for equal expansion of the number of subjects into each of these cohorts. Details regarding the randomization technique(s) will be detailed in the SAP. On Day 1 Pre-Dose, after confirming the subject's eligibility, the Investigator (or his designee) will approve the subject's unblinded randomization. Subjects will be randomized in a fashion that will maintain a balance between the 2 cohorts across all subjects enrolled (not per site) and notify the site of the result.

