17.7.4. Face Subpopulation

Subjects whose Treatment Fields are located on their face (i.e., cheeks or forehead) will constitute the ITT-Face, mITT-Face, and PP-Face populations.

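### The Safety population is limited to randomized subjects, which excludes about 80 of 150 planned subjects, and Section 17.4 uses an ITT population that is not defined

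*Combined protocol and SAP*

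**What the plan says.** Section 17.7.1 sets two conditions for the safety analysis set: "The Safety population will be defined as all subjects who are randomized and who receive study drug". Its next sentence assigns the safety analyses to that set.

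Section 12.1.2 describes consecutive enrolment into Part A (Cohort 1) and Part B (Cohort 2) and adds: "There will be no need for randomization in Part A or Part B". Randomization starts in Part C, where, according to Section 5.6.4, "70 subjects will be randomized in a 1:1 ratio to either Cohort 1 or Cohort 2".

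Two other places name the set for the safety summaries, and they disagree:

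- Synopsis, Safety Analysis: "The safety endpoint data will be summarized for the Safety Population".
- Section 17.4: "The safety endpoint data will be summarized for the ITT population".

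Section 17.7 defines Safety, mITT, Per Protocol and Face sets. It does not define an ITT set, although Section 17.7.4 says that subjects with facial fields "will constitute the ITT-Face, mITT-Face, and PP-Face populations". The mITT definition in Section 17.7.2 is built on enrolment, not randomization: "all subjects who are enrolled into the study, received any study drug", with a further condition about Exclusion Criterion #2.

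Section 17.1 gives the purpose of enrolling about 75 per cohort: to "complete each cohort with safety and efficacy data from at least 70 subjects who received study drug".

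**The concern.** A subject in Part A or Part B is never randomized and so cannot meet the Section 17.7.1 definition, however long that subject is treated. More than half of the planned subjects would be missing from the safety tables. They would not be a random half either: they are all the subjects enrolled before Part C opened.

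Turning to Section 17.4 does not help, because the set it names has no definition. The programmer has one set that is too small and another that does not exist.

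Safety and tolerability is a primary objective (Section 6), and Section 5.6.4 says the results will feed Phase 3 design and dose selection. There is no control arm and the summaries are descriptive, so the denominator largely determines what can be said about tolerability. Under the literal definition, clearance would be reported on up to about 75 subjects per cohort, but adverse events and local skin reactions on only about 35 of them. The benefit and the tolerability of each regimen would then not be described on the same group.

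**Working it through.** **Inputs**

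- Part A: about 40, not randomized (Synopsis; Sections 5.6.4 and 12.1.2).
- Part B: about 40, not randomized (same places).
- Part C: 70, randomized 1:1 (same places).
- Planned total about 150, about 75 per cohort, at least 70 per cohort with safety data (Section 17.1).
- No formal sample size calculation was done (Section 17.1), so there is no power figure to reproduce.

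**1. The plan's own totals**

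- Total: 40 + 40 + 70 = 150.
- Per cohort: 40 + 70/2 = 75.

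Both agree with Section 17.1.

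**2. The Safety population under Section 17.7.1 as written**

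- Excluded: 40 + 40 = 80, and 80/150 = 53.3%.
- Kept: 70 in total, or 70/2 = 35 per cohort, and 35/75 = 46.7%.
- Against the Section 17.1 minimum: 35/70 = 50%.

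The mITT set, based on enrolment, could reach about 150. The efficacy set would be roughly twice the Safety set (150/70 = 2.1).

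**3. What the smaller denominator does (illustration)**

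The plan specifies no confidence intervals for adverse events, and the event rates below are assumptions. With zero events among *n* subjects, the two-sided 95% Clopper-Pearson upper bound is 1 − 0.025^(1/n). The chance of seeing at least one case at true rate *p* is 1 − (1 − p)^n.

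| Subjects per cohort | Upper bound, 0 events | At least one case, p = 1% | p = 2% | p = 5% |
|---|---|---|---|---|
| 35 (17.7.1 as written) | 10.0% | 29.7% | 50.7% | 83.4% |
| 75 (all enrolled) | 4.8% | 52.9% | 78.0% | 97.9% |

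At the planned minimum of 70 the upper bound is 5.1%.

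**4. Which set the safety summaries use**

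| Place | Set named | Usable as written? |
|---|---|---|
| Synopsis, Safety Analysis | Safety | Only through 17.7.1, which excludes Parts A and B |
| Section 17.7.1 | Safety | Defined, but covers Part C only |
| Section 17.4 | ITT | No: not defined in Section 17.7 |

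Otherwise, ITT appears only in the abbreviation list, in the account of the earlier Phase 2 trial, and in the ITT-Face label of Section 17.7.4. The efficacy analyses in Sections 17.3.1 and 17.3.2 use mITT, PP and their Face subsets, so no listed analysis uses ITT-Face.

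**The case against.** The best defence is that the intent can be recovered. The 70-per-cohort target in Section 17.1 cannot be met by a randomized-only set. The Synopsis and Section 17.7.1 both name the Safety population, so Section 17.4 is the outlier. The protocol also uses the word randomization loosely elsewhere: Section 13.6.3 places it after the Day 1 Pre-Dose training test without limiting it to Part C. On that reading, randomized in Section 17.7.1 simply means enrolled, and nobody plans to drop 80 treated subjects. Section 17.2 lists all variables individually and defers analysis details to the SAP, so no data would be lost and a later document could settle the point.

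Most of this is fair. The wording is probably carried over, the effect is confined to summary tables, and the precision figures describe the literal rule rather than an outcome anyone seems to want. Two qualifications are also right. The literal Safety set would be almost wholly a subset of the efficacy set rather than a separate group. And ITT is undefined in the documents supplied, which contain no further SAP text that might define it.

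None of this makes the definition correct. Section 12.1.2 separates consecutive enrolment from random assignment, and Section 17.7.2, the very next definition, uses enrolment. An analysis set for a primary objective should not depend on the programmer guessing which word was meant. Deferral to the SAP is a reason to correct the source text, so that the error is not copied forward.

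**Conclusion.** The concern holds. As written, the Safety population covers about 70 of 150 planned subjects (35 per cohort) and excludes the 80 in Parts A and B. The alternative named in Section 17.4 has no definition in these documents. The counts rest on the approximate planned part sizes and on everyone enrolled being dosed, so actual numbers will differ somewhat. The conflict itself does not depend on them. Data collection and the individual listings are unaffected; the denominators of every safety summary table are affected.

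**What to change.** Three wording edits:

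1. **Section 17.7.1.** Define the Safety population as all enrolled subjects in Parts A, B and C who receive at least one application of study drug, summarized by cohort as the plan already intends.
2. **Section 17.4.** Name the Safety population in place of ITT, in line with the Synopsis and Section 17.7.1.
3. **Section 17.7.4.** Delete ITT-Face, or add a definition of ITT to Section 17.7 if that set is wanted.

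Carry the same definitions into the SAP before database lock. The corrected set would be up to about 75 per cohort, which fits the Section 17.1 target. It can still differ slightly from mITT, because mITT also removes subjects who fail Exclusion Criterion #2. The edits do not change visits, data collection or sample size.
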